### 5.1.2 Visit Windows

Any efficacy analysis that utilizes time to event approach will be based on an exact determination of time from C1D1 to the date of event/censoring.

Unless otherwise stated data will be presented as collected on the nominal visits, that is, if data are collected as part of CxDy visit in the CRF it will be presented as such in analyses irrespective of the subject's adherence to the protocol visit schedule and actual collection date. Unscheduled visits will not be displayed summaries but will be listed.

Disease assessments are not tied to nominal visits in eCRF but are scheduled to be performed on a regular basis per protocol. The analysis time window listed in Table 4 and Table 5 will be used to slot actual disease assessment date into planned disease assessment schedules for summary statistics for RRMM, AML and R/R DLBCL, respectively. The visit window is mainly for display disease assessment in a chronological order and will generally not be used in actual analysis.

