#### Expansion:

- Table 1-5 Schedule of Activities – Subjects With RRMM – Expansion Part A (GEN3014 Single Cohorts)
- Table 1-6 Schedule of Activities – Subjects With R/R AML – Expansion Part A (GEN3014 Single Cohorts)
- Table 1-7 Schedule of Activities – Subjects With R/R DLBCL – Expansion Part A (GEN3014 Single Cohorts)
- Table 1-8 Schedule for PK, Biomarker/Pharmacodynamic, and Immunogenicity Sampling – All Subjects – Expansion Part A (GEN3014 Single Cohorts)
- Table 1-9 Minimal Residual Disease CCI Evaluation Schedule – Subjects with RRMM – Expansion Part A (GEN3014 Single Cohorts)
- Table 1-10 Minimal Residual Disease Schedule – Subjects with R/R AML – Expansion Part A (GEN3014 Single Cohorts)
- Table 1-11 Minimal Residual Disease CCI Evaluation Schedule – Subjects with R/R DLBCL – Expansion Part A (GEN3014 Single Cohorts)
- Table 1-12 Schedule of Activities – Subjects with RRMM – Expansion Part B (Randomized H2H)
- Table 1-13 Schedule for PK, Biomarker/Pharmacodynamic, and Immunogenicity Sampling – GEN3014 IV-Treated Subjects – Expansion Part B (Randomized H2H)
- Table 1-14 Schedule for PK, Biomarker/Pharmacodynamic, and Immunogenicity Sampling – Daratumumab SC-Treated Subjects – Expansion Part B (Randomized H2H)
- Table 1-15 Minimal Residual Disease CCI Evaluation Schedule – Subjects with RRMM – Expansion Part B (Randomized H2H)

In addition to the fixed visits, it may be necessary to perform some of the assessments at unscheduled time points if deemed clinically necessary by the investigator.

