    - g. Grade 3 diarrhea that responds to adequate antidiarrheal treatment in  $\leq 3$  days

- h. Grade 3 fatigue/asthenia when fatigue/asthenia was present at baseline or that lasts for <14 days
- i. Alopecia (all grades)
- Grade 4 TLS (see Section 10.3.7 for additional information)
- Grade 4 IRR
- Any liver toxicity of elevated ALT or AST  $\geq 3$  times or greater above the upper limit of normal (ULN) with serum total bilirubin of  $\geq 2$  times the upper limit of normal, without findings of cholestasis and in the absence of alternative etiologies

**Note:** AEs of specified grades, regardless of relationship to GEN3014, should be considered relevant for dose escalation decisions, unless the event can clearly be determined to be unrelated to the drug. All of the AEs of specified grades should be classified as DLTs except those that are clearly and incontrovertibly due to the underlying disease or extraneous causes.

The investigator must notify the sponsor immediately of a DLT. Frequent laboratory monitoring of complete blood count (CBC) including differential should be initiated to document start and resolution of hematological AEs. All AEs occurring during the defined DLT evaluation period will be assessed according to the criteria above. All GEN3014-related AEs will be monitored and included in the evaluation of the toxicity profile of GEN3014 unless the event is clearly determined to be unrelated to GEN3014 (eg, disease progression).

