### **5.5.4      *Additional Safety Assessments (if applicable)***

#### **5.5.4.1      *Clinical Laboratory Data***

Grading of laboratory values will be assigned programmatically as per CTCAE v5.0. The calculation of CTCAE grades will be based on the observed laboratory values only; clinical assessments will not be considered.

CTCAE Grade 0 will be assigned for all non-missing values not graded as 1 or higher.

For laboratory tests where grades are not defined by the CTCAE, results will be categorized as low/normal/high based on laboratory normal ranges.

The following summaries will be generated separately for hematology and biochemistry tests:

- Listing of laboratory data with values flagged to show the corresponding CTCAE term and CTCAE grades, if applicable, and the classifications relative to the laboratory normal ranges.

For laboratory tests where grades that are defined with a CTCAE term:

- Worst post-baseline on-treatment CTCAE grade (regardless of the baseline status). Each subject will be counted only once for the worst grade observed post-baseline.
- Shift tables using CTCAE grades to compare baseline to the worst on-treatment value.
- Summary table of Grade 3 or higher CTCAE graded laboratory toxicities

For laboratory tests where grades are not defined by a CTCAE term:

- Shift tables using the “low/normal/high” classification to compare baseline to the worst on-treatment value

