#### **5.5.4.2      *Vital Signs***

The number and percentage of subjects meeting the below criteria at any post-baseline assessment will be summarized by cohort.

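### SAP 5.1.2 keeps unscheduled visits out of summaries without exception, in conflict with the worst-value and any-time safety tables of SAP 5.5.4

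*SAP*

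**What the plan says.** SAP 5.1.2 (Visit Windows) opens its rule on presentation with a default: "Unless otherwise stated data will be presented as collected on the nominal visits". It goes on to say that the visit recorded in the case report form decides, whatever the actual date. The next sentence reads: "Unscheduled visits will not be displayed summaries but will be listed". A word is missing, but the meaning is that unscheduled visits go to listings only.

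The safety tables are defined in SAP 5.5.4:

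- Laboratory worst grade (5.5.4.1): "Each subject will be counted only once for the worst grade observed post-baseline".
- Laboratory shifts (5.5.4.1): "Shift tables using CTCAE grades to compare baseline to the worst on-treatment value".
- Vital signs (5.5.4.2): "The number and percentage of subjects meeting the below criteria at any post-baseline assessment will be summarized by cohort". The same sentence introduces the QTcF criteria in 5.5.4.3, under a label for the highest post-baseline interval.

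The protocol foresees unscheduled readings. Section 1.3 says that "it may be necessary to perform some of the assessments at unscheduled time points if deemed clinically necessary by the investigator", and the schedules of activities mark hematology, biochemistry, vital signs and ECG in their unscheduled column. For Dose Escalation, protocol 6.6.1 adds: "Frequent laboratory monitoring of complete blood count (CBC) including differential should be initiated to document start and resolution of hematological AEs".

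**The concern.** Unscheduled readings are not a random sample of the data. They are taken when the investigator sees a clinical need, so they are more likely than scheduled readings to hold a subject's worst value. A programmer who follows 5.1.2 to the letter would leave them out of the tables meant to show worst values. Another, following 5.5.4, would include them. Both could cite the SAP, and the two sets of safety tables would differ.

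Changes in laboratory values, vital signs and ECGs belong to a primary endpoint in Dose Escalation and a secondary endpoint in both expansion parts (protocol Tables 3-1 to 3-3). The laboratory tables also serve a separate purpose. Grades are assigned by program from observed values, without clinical assessment, which gives a check on toxicity that does not depend on what an investigator chose to report. Dropping the unscheduled values weakens that check. In Expansion Part B, if one arm had more toxicity-driven sampling, the exclusion would tend to shrink the observed difference between arms.

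**Working it through.** The SAP states no figure that depends on this rule, so there is none to reproduce. The check sets the texts side by side and then asks what can be said about direction and size.

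**1. Scope of the rule.** The 5.1.2 sentence on unscheduled visits has no qualifier. The *unless otherwise stated* clause belongs to the sentence before it, on nominal visits.

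**2. Scope of the tables.**

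| Output | Where | Values it calls for | Under literal 5.1.2 |
|---|---|---|---|
| Worst laboratory grade | SAP 5.5.4.1 | worst post-baseline, on treatment | scheduled only |
| Laboratory shift | SAP 5.5.4.1 | worst on treatment | scheduled only |
| Grade 3 or higher laboratory | SAP 5.5.4.1 | not specified | scheduled only |
| Notable vital signs | SAP 5.5.4.2 | any post-baseline | scheduled only |
| QTcF outliers | SAP 5.5.4.3 | any or highest post-baseline | scheduled only |

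None of these definitions limits the values to scheduled visits. SAP 5.1.1.2 sets the on-treatment period by dates, so an unscheduled reading falls inside it.

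**3. Protocol and declared changes.** Protocol 9.4.5.2 plans the worst post-baseline CTCAE grade, also without a visit limit. SAP 6.1 declares no change to protocol-planned analyses. Literal use of 5.1.2 would therefore be an undeclared change. The SAP was written against Global Amendment 3 and the protocol at hand is Amendment 5, so this step assumes that 9.4.5.2 read the same way in Amendment 3.

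**4. Is safety data protected elsewhere?** The text after SAP Table 5 says that windowing should not cause data to be disregarded for efficacy. There is no matching sentence for safety.

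**5. Direction.** Let S be a subject's scheduled post-baseline readings and U the unscheduled ones. Then max grade over S ≤ max grade over S ∪ U. A subject who meets a criterion somewhere in S also meets it somewhere in S ∪ U. With baseline held fixed, leaving out U can lower a worst grade or an outlier count but never raise it.

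**6. Size.** Hematology and biochemistry are scheduled on dosing days, so the interval I is 7 days in Cycles 1-2, 14 in Cycles 3-6 and 28 from Cycle 7. Assume an abnormality stays at a given grade for L days with random onset; neither L nor the onset pattern is in the documents. The chance that a scheduled sample catches it is c = min(1, L/I), and the chance that it is missed is 1 − c:

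- L = 7: c = 7/7, 7/14, 7/28 = 1.0, 0.50, 0.25; missed 0, 0.50, 0.75.
- L = 4: c = 4/7, 4/14, 4/28 = 0.57, 0.29, 0.14; missed 0.43, 0.71, 0.86.

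The loss caused by the rule is (1 − c) × u, where u is the share of missed episodes in which an unscheduled sample was taken at that grade. An episode never sampled is absent under either reading. The documents do not give u, so it can lie anywhere from 0 to 1. For 7-day episodes the loss lies between 0 and 0.50 in Cycles 3-6 and between 0 and 0.75 from Cycle 7. These are ceilings per episode. The tables count each subject once, so a lost later episode changes nothing if the subject already had that grade at a scheduled visit.

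The protocol's estimated treatment of 4 months for myeloma and DLBCL (4.4.1) is 4 × 30.4375 / 28 ≈ 4.3 cycles, so the Cycle 3-6 ceiling is the more relevant of the two.

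**The case against.** The strongest reply is that the sentence concerns display, not derivation. It sits under visit windows and closes a paragraph on nominal-visit presentation, so it may mean only that unscheduled visits get no row or column in by-visit tables. The specific sections can be read as stating otherwise. A universal reading also sits badly with the assurance that windowing removes no efficacy data. Protocol 9.4.5.2 and the absence of declared changes in SAP 6.1 point towards inclusion as well. Programming notes are kept in the Data Presentation Specification, which is not available here and may settle the matter.

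Much of this stands. A reader might infer that the SAP definitely removes unscheduled readings from every safety table. The documents do not support that, and inclusion may well be what was meant. A reader might also infer that half to three quarters of one-week episodes after Cycle 2 would be lost. That is not supported either: those figures are the chance of missing a scheduled sample under assumed durations, not the loss caused by the rule. Moreover, the explicit call for frequent blood counts is in the Dose Escalation section on dose-limiting toxicity, whose evaluation period is Cycle 1. Sampling there is weekly, and a 7-day episode would be caught anyway.

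Other outputs also hold part of the information. Clinically significant laboratory abnormalities are recorded as adverse events (protocol 10.3.3.1). Treatment-emergent event tables follow onset dates, the expansion stopping guidance uses adverse events and deaths, and unscheduled laboratory values remain in graded listings.

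Two things remain. No text says that 5.5.4 overrides 5.1.2. And adverse-event tables do not fully replace laboratory tables, because protocol 8.3.6 generally treats findings associated with the underlying disease as not clinically significant unless they are worse than expected. That leaves many cytopenias in myeloma and AML to judgment.

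**Conclusion.** The point holds as an unresolved conflict between a general rule and specific table definitions. It is not a demonstrated exclusion. The direction of any error is certain if 5.1.2 is applied literally and baseline is unchanged: reported laboratory, vital-sign and QTcF toxicity can only fall. The size cannot be derived from the documents. The 50% and 75% figures are ceilings that assume 7-day episodes, random onset and an unscheduled sample in every missed episode; the lower limit is zero. This should be fixed before the safety tables are programmed. It does not undermine the trial's other safety outputs.

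**What to change.** Replace the sentence on unscheduled visits in SAP 5.1.2 with:

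> Unscheduled assessments are not shown in by-visit summaries; worst-grade, shift, Grade 3 or higher, notable-value and QTcF outlier summaries use all post-baseline on-treatment assessments, scheduled and unscheduled.

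Bring the Data Presentation Specification into line if it says anything different. If the sponsor does intend to exclude unscheduled readings from these tables, SAP 6.1 should record that as a change from protocol 9.4.5.2, with the reason. The cost is one sentence and no new data, since the readings are already to be listed.

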**Table 4: Analysis visit windows for efficacy summary listings in RRMM and AML**

Analysis period	Target day (visit window per protocol)	Analysis visit window	Label on output
Baseline	1 (pre-dose C1D1)	Last data point prior to dosing	Baseline
Baseline for SPEP and UPEP (RRMM)	1 (-3 to 1)	Last data point prior to dosing	Baseline
Scheduled on-treatment disease assessments every 28 days	28 ( $\pm 3$ )	1 to 42	Week 4
	56 ( $\pm 3$ )	42 to 70	Week 8
	...	...	...
Unscheduled	-	-	Unscheduled <Day x>
End of treatment	-	-	End of treatment

**Table 5: Analysis visit windows for efficacy summary listings in R/R DLBCL**

Analysis period	Target day (visit window per protocol)	Analysis visit window	Label on output
Baseline	1 (pre-dose C1D1)	Last data point prior to dosing	Baseline
Scheduled on-treatment disease assessments Week 6,	42 ( $\pm 3$ )	1 to 63	Week 6
	84 ( $\pm 3$ )	64 to 105	Week 12

12, 18, and 24, then every 24 weeks thereafter	126 ( $\pm$ 3)	106 to 147	Week 18
	168 ( $\pm$ 3)	148 to 252	Week 24
	336 ( $\pm$ 3)	253 to 420	Week 48
	...	...	...
Unscheduled	-	-	Unscheduled <Day x>
End of treatment	-	-	End of treatment

Response assessments should be performed until confirmation of disease progression, start of new anti-cancer therapy, withdrawal of consent, or death, whichever comes first.

Details on how to slot subject data that systematically is performed off schedule is provided in the ADaM specification, but no data should be disregarded for efficacy evaluations due to this windowing.

### 5.1.3 *Disease Specific Response Considerations*

Each individual timepoint response per disease specific criteria is reported by investigator in eCRF. The best overall response (BOR) will be derived for the purpose of analyzing efficacy endpoints (ORR, DOR and CBR). Timepoint responses recorded after new anticancer therapy or progressive disease (PD), will be excluded from BOR derivation. Section 5.1.3.1 to 0 details disease specific derivations.

#### 5.1.3.1 *Considerations Related to IMWG 2016*

##### **Baseline measurable disease**

Baseline measurable disease in RRMM subjects is defined as:

- IgG, IgA, IgD, or IgM myeloma: Serum M-protein level  $\geq 0.5$  g/dL ( $\geq 5$  g/L) or urine M-protein level  $\geq 200$  mg/24 hours

or

- Light chain myeloma: Serum Ig free light chain (FLC)  $\geq 10$  mg/dL and abnormal serum Ig kappa lambda FLC ratio.

RRMM subjects should also provide documentation of monoclonal plasma cells in the bone marrow  $\geq 10\%$  or presence of a biopsy-proven plasmacytoma.

##### **Key response variables**

Response to GEN3014 or daratumumab SC in RRMM subjects will be assessed in accordance with the IMWG Response Criteria (Kumar et al., 2016). Centrally analyzed samples will be used by the investigator to report the response in eCRF. The best overall response in RRMM subjects can be one of sCR, CR, VGPR, PR, MR, SD, PD or NE.

To support the responses based on the IMWG criteria, a detailed efficacy listing with below parameters is planned:

- SPEP as measured by the total amount of abnormal protein in the serum electrophoresis. (This may constitute one or more abnormal spikes in different protein bands.)
  - With IFE interpretation of the serum
- UPEP as measured by the total amount of abnormal protein in the urine electrophoresis
  - With IFE interpretation of the urine
- FLC with the kappa to lambda ratio, and the difference between the two chains
- The sum of the product of the perpendicular diameters (SPD) of the plasmacytomas (or longest diameter if only 1 is reported)
  - Radiated plasmacytomas are not evaluable for response, and can only be used to monitor progression
- Bone marrow plasma cells, as assessed by aspiration and/or biopsy.
  - If both aspiration and biopsy is obtained at same time point the highest value will be used
- Lytic bone lesions are used only to assess progression
  - In particular, the bone lesion eCRF assessment form will be used to assess progression with the two questions *Is there definite increase in the size of existing bone lesions since baseline?* and *Is there development of new bone lesions since baseline?*
  - For descriptive purposes only, the number of bone lesions will be reported as follows: The number of lytic lesions is assessed on the skeletal eCRF assessment form, and reported as 0, 1, 2, 3, >3, or “Unable to Determine” per anatomic location. The following rules are applied when deriving the total number of bone lesions:
    - If no anatomic location has “>3” or “Unable to Determine”: sum the numerical values and sort into one of the following categories: “0”, “1-3”, or “4-10” or “>10”
    - If one or more anatomic location(s) has “>3” or “Unable to Determine”: the total number of lytic bone lesions is set to “Unable to Determine”

#### 5.1.3.2 Considerations Related to Lugano

The protocol categorizes lesions as measurable (nodes, or target), and non-measurable (or non-target) sites. For analysis purposes target and non-target lesions will be referred.

For subjects with FDG-avid tumors at Screening, all subsequent disease assessments will be performed with FDG-PET CT using the 5-point scale. That is, at each time point, the most metabolically active lesion is assessed using the 5-point scale (Van Heertum et al., 2017), and this will determine the overall time point response per Table 6.

**Table 6: PET based response**

Response	Target lesions (Nodes/measurable)	Non-target lesion (extranodal/non-measurable)	Organ Enlargement	New Lesions	Bone Marrow
Complete Response (CR)	Score 1, 2 or 3 with or without a residual mass on 5PS a	Not applicable	Not applicable	None	No evidence of FDG-avid disease in marrow
Partial Response (PR)	Score 4 or 5 with reduced uptake compared to baseline and residual mass of any size	Not applicable	Not applicable	None	Residual uptake higher than uptake in normal marrow but reduced compared to baseline
No response or Stable Disease (SD)	Score 4 or 5 with no significant change in FDG uptake	Not applicable	Not applicable	None	No change from baseline
Progressive disease (PD)	Score 4 or 5 with an increase in intensity of uptake	None		New FDG-avid foci consistent with lymphoma	New or recurrent FDG-avid foci

For subjects with non-avid or variably FDG-avid tumors, CT scan with IV contrast of neck/chest/abdomen/pelvis/additional known lesions will be performed. The overall time point response based on the CT scans will be categorized per Table 7.

**Table 7: Response Criteria – CT/MRI Scan**

Response	Lymph Nodes	Non-measurable Lesion	Organ Enlargement	New Lesions	Bone Marrow
Complete Response (CR)	Target nodes/nodal masses regression ≤1.5 cm in longest diameter	Absent	Regress to normal	None	Normal by morphology
Partial Response (PR)	≥50% decrease in SPD of up to 6 target measurable nodes and extranodal sites	Absent/normal, regressed, but no increase	Spleen regressed >50% in length beyond normal (13 cm)	None	Not applicable
No response or Stable Disease (SD)	<50% decrease in SPD of up to 6 target measurable nodes and extranodal sites	No increase consistent with progression	No increase consistent with progression	None	Not applicable
Progressive disease (PD)	>1.5 cm and increase by ≥50% from nadir and increase from nadir 1. 0.5 cm for lesions ≤2 cm 2. 1.0 cm for lesions >2 cm	New or clear progression of pre-existing lesions	Spleen length increase of >50%	New nodes >1.5 cm New extranodal site >1.0 cm Assessable disease of any size attributable to lymphoma	New or recurrent involvement

## 5.2 Subject Dispositions

Subject dispositions will be presented in flow diagrams in accordance with the current CONSORT statement.

The number of subjects in each analysis set will be tabulated as defined in Section 0 for all enrolled subjects. Frequencies and percentages of subjects who discontinued treatment or discontinued from trial, along with the primary reason for discontinuation will be provided for the FAS.

Time to treatment discontinuation in Expansion Parts A and B, will be presented graphically using a stacked cumulative incidence function accounting for competing risks (e.g., treatment discontinuation due to the reasons as collected in the eCRF). Time to treatment discontinuation and time to trial discontinuation will be estimated using Kaplan-Meier methods.

A by-subject listing will be generated to provide disposition status and early discontinuation reason.

## 5.3 Primary Endpoint(s) Analysis

### **Dose Escalation**

The primary endpoints in the Dose Escalation phase are the DLTs (presented based on the DDS), general AEs and safety laboratory parameters (presented based on the FAS/SAF). Safety analyses are described in Section 5.5.

### **Expansion Parts A and B**

The primary endpoint of the Phase 2 Expansion is the objective response rate (ORR) per disease specific criteria, as assessed by investigator. There is no pre-specified hypothesis that is to be tested.

#### ***5.3.1 Definition of Endpoint(s)***

ORR is defined as the proportion of subjects in the analysis population (FAS is used for primary analysis) with a BOR of partial response (PR) or better according to the disease specific criteria. In detail, the disease-specific definitions of ORR are

- RRMM: a BOR of PR, VGPR, CR or sCR
- R/R DLBCL: a BOR of PR or CR
- R/R AML: a BOR of MLFS, PR, CRp, CRi, or CR.

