**Specific Exclusion Criteria for R/R AML:**

16. <5% blasts in blood or bone marrow at Screening.
17. Prior autologous HSCT.
18. Allogenic HSCT within 3 months of the first dose of GEN3014.
19. Criterion modified per Amendment 1.
  - 19.1 Active graft-versus-host-disease requiring immunosuppressive treatment. Any immunosuppressive medication (eg, calcineurin inhibitors) must be stopped  $\geq 4$  weeks prior to the first dose of GEN3014.

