#### **9.4.3.1 Objective Response Rate and Clinical Benefit Rate**

ORR is defined as the proportion of subjects with a partial response, or better. Summaries of eg, VGPR and CBR will be provided with ORR as appropriate.

Disease-specific best overall response (BOR) will be summarized in conjunction with the ORR. The estimated rates and the exact 2-sided 95% confidence intervals (CI) (using the Clopper-Pearson method) will be summarized. Individual subject data listings will be provided.

The ORR for subjects treated with GEN3014, as compared to the ORR in subjects treated with daratumumab SC in the Expansion Part B with anti-CD38 mAb-naïve RRMM subjects, will be presented by the response ratio and the corresponding 2-sided 95% confidence interval based on the Miettinen-Nurminen method ([Newcombe, 1998](#)). P values will not be presented.

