#### Peripheral blood counts:

No circulating blasts  
Neutrophil count  $< 1.0 \times 10^9/L$ , or platelet count  $< 100 \times 10^9/L$   
Transfusion independence is not required.

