### Morphologic Leukemia-Free State (MLFS):

#### Bone marrow aspirate and biopsy:

≤5% blasts  
No Auer rods  
No extramedullary leukemia

**Treatment Failure:** Failure to achieve at least a PR

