### Relapse from CR, CRi, CRp or PR:

- Relapse after CR, CRi, or CRp is defined as the reappearance of leukemic blasts in the peripheral blood or  $\geq 5\%$  of blasts in the bone marrow aspirate not attributable to any other cause, or reappearance or new appearance of extramedullary leukemia.
- Relapse after PR is similarly defined with the reappearance of significant numbers of peripheral blasts and an increase in the percentage of blasts in the bone marrow aspirate to  $> 25\%$  not attributable to any other cause, or reappearance or new appearance of extramedullary leukemia.

Source: ([Cheson et al., 2003](#)).

**10.12 Appendix 12:** CCI

CCI

**Table 10-4** CCI

CCI

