#### ***IWG -R/R AML***

CR	Complete remission (included in ORR)
CRi	Complete remission with incomplete hematological recovery (included in ORR)
CRp	Complete remission with incomplete platelet recovery (included in ORR)
PR	Partial remission (included in ORR)
MLFS	Morphologic leukemia-free state (included in ORR)
SD	Stable disease
DP	Disease progression
R	Relapse

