***or***
- for subjects who's response to last prior therapy was complete remission:
  - bone marrow aspirate and/or biopsy blasts  $\geq 5\%$ , or
  - reappearance of blasts in the blood, or

- development of extramedullary AML.

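### AML objective response counts MLFS, which the protocol defines without any blood condition, and the 5% marrow limits for response and relapse overlap

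*SAP*

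**What the plan says.** **Responder definition.** SAP Section 5.3.1 lists "R/R AML: a BOR of MLFS, PR, CRp, CRi, or CR", and the SAP's list of response abbreviations also marks MLFS as part of ORR. ORR is the only primary endpoint of the AML expansion cohort (N=20, SAP Section 3). It is assessed by the investigator, and the primary analysis uses the FAS.

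**Protocol definition.** Protocol Section 9.4.3.1 states: "ORR is defined as the proportion of subjects with a partial response, or better". Appendix 11 (Section 10.11) prints MLFS after PR and defines treatment failure as not reaching at least PR.

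**Blood conditions.** In Appendix 11, CR, CRi and CRp each require that no blasts circulate. For CRi and CRp it adds: "Transfusion independence is not required". MLFS has no peripheral-blood block.

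**Relapse and entry.** Appendix 11 says: "Relapse after CR, CRi, or CRp is defined as the reappearance of leukemic blasts in the peripheral blood or" at least 5% blasts in the marrow. Protocol Section 5.2.1, exclusion 16, removes subjects with "<5% blasts in blood or bone marrow at Screening". Inclusion 18.2 in Section 5.1.2 sets relapse at marrow blasts of 5% or more, or blasts in the blood, or extramedullary AML.

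**Declared changes.** SAP Section 6.1, on changes to protocol-planned analyses, reads as not applicable.

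**The concern.** A response category with no blood criterion can be met by a subject whose blood still carries blasts, provided the marrow is at or below 5%. Appendix 11 treats the return of such blasts as relapse after CR, CRi or CRp. The SAP counts this category in the primary endpoint, where the protocol asks for PR or better.

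The marrow limits also meet at one value. At exactly 5%, a subject is at the entry and relapse limit and at the response limit together.

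With 20 subjects and a single primary endpoint, one or two such classifications would visibly change the reported ORR.

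**Working it through.** The plan gives no target ORR, power or error rate for the AML cohort, so there is no figure to reproduce. The check is a comparison of definitions, followed by the effect of one subject.

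**Step 1. The Appendix 11 categories side by side.** Counts are ×10⁹/L.

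| Category | Marrow blasts | Blood blasts | Neutrophils | Platelets | Transfusion |
|---|---|---|---|---|---|
| CR | ≤5% | none | ≥1.0 | ≥100 | none for 1 week |
| CRi | ≤5% | none | <1.0, or platelets <100 | see left | allowed |
| CRp | ≤5% | none | ≥1.0 | <100 | allowed |
| PR | 5–25% with ≥50% reduction, or <5% with Auer rods | none or a few | ≥1.0 | ≥100 | not stated |
| MLFS | ≤5% | not stated | not stated | not stated | not stated |

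CR, CRi, CRp and MLFS also require no Auer rods and no extramedullary leukaemia.

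**Step 2. What MLFS adds.** Take a subject who meets the shared marrow rule.

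- Blood clear, neutrophils <1.0 or platelets <100: CRi (or CRp).
- Blood clear, counts recovered, no transfusion for a week: CR.
- Blood clear, counts recovered, transfused within the week: not CR, CRi or CRp, so MLFS.
- Blasts in the blood, at any level and with any counts: not CR, CRi or CRp, so MLFS.

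Only the last two groups are new to ORR through MLFS. One edge case overlaps with PR: a subject at exactly 5% after at least a 50% reduction, with recovered counts and at most a few blood blasts, is PR already.

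**Step 3. The 5% limit.** Entry on marrow allows b ≥ 5 (only b < 5 is excluded). Response needs b ≤ 5. The two sets share one value, b = 5. A subject at 5% before and on treatment, without Auer rods or extramedullary disease, meets MLFS unchanged. With clear blood and low counts, the same subject meets CRi. The relapse limit (≥5%) is met at the same visit.

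**Step 4. Does anything else close the gap?** SAP Section 5.1.3 announces disease-specific derivations but gives them only for the myeloma and lymphoma criteria. Protocol Section 8.2.2 says that AML response rests on blood and marrow, without setting a blood criterion for MLFS. SAP Section 5.3.3 plans no sensitivity analysis. Appendix 11 has no rule for relapse after MLFS, while SAP Section 5.4.3 limits DOR to PR or better. It is therefore unstated whether MLFS subjects enter DOR and what would end their response.

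**Step 5. Size.** ORR = x/20, so one subject is 1/20 = 5 percentage points. The 95% Clopper-Pearson limits are the 2.5% point of Beta(x, 21−x) and the 97.5% point of Beta(x+1, 20−x).

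| x | ORR | 95% CI |
|---|---|---|
| 0 | 0% | 0–16.8% |
| 1 | 5% | 0.1–24.9% |
| 2 | 10% | 1.2–31.7% |
| 3 | 15% | 3.2–37.9% |

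As an example, if one of three recorded responders were MLFS only, ORR without MLFS would be 2/20 = 10% rather than 15%.

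**The case against.** Several counter-arguments have force.

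- **Investigators assign the response.** They use blood, marrow and extramedullary findings together, and stable disease, progression and relapse are available categories. An investigator may never record MLFS for a blast-positive subject. This stands: such a subject could be recorded as a responder, not must be. For the same reason, a zero or undefined DOR at 5% is possible but does not follow automatically.
- **The MLFS count will be visible.** SAP Section 5.3.2 reports every response category, so ORR without MLFS can be found by subtraction. This stands, but the headline ORR still includes MLFS, and that table does not show which MLFS subjects had blood blasts.
- **PR tolerates a few circulating blasts.** True, so blood blasts alone do not rule out response in this protocol. PR still caps them at a few and requires neutrophil and platelet recovery. MLFS does neither.
- **The SAP may be filling in detail.** The protocol lists no AML categories for ORR, does not rank MLFS explicitly, and defers detail to the SAP. MLFS also has a deeper marrow result than PR. The SAP cites protocol version 5.0, not the current 8.0. These points explain how the difference could have arisen, but they do not remove it: the current texts disagree and no change is declared.

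A reader might go further and infer that subjects who enter on blood blasts alone meet MLFS before the first dose. That depends on how exclusion 16 is read. If marrow below 5% excludes, such subjects do not enter unless the marrow is exactly 5%. The route opens only if blasts in either site suffice. SAP Section 4.2, which accepts "reappearance of blasts in the blood, or" other findings after a prior remission, defines the response evaluable set. It is not an entry rule, and the primary ORR uses the FAS.

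A reader might also infer that MLFS adds mainly blast-positive subjects. The documents give no basis for saying whether that group or the transfused group is larger.

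**Conclusion.** The AML primary endpoint is wrong as written in two respects.

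1. MLFS counts as response without a blood condition. Beyond CR, CRi and CRp, it brings in only recently transfused subjects with recovered counts and subjects with circulating blasts at any level. On a plain reading, this is wider than the protocol's PR or better, and it is undeclared.
2. At exactly 5% marrow blasts, the response limit overlaps the entry and relapse limits, so an unchanged subject could be recorded as a responder. This is confined to that single value. It is shared by CR, CRi and CRp, so it is not a defect of MLFS alone.

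Each affected subject adds 5 percentage points at N=20. The number affected cannot be derived from the documents and may be zero. The cohort is described as hypothesis generating (protocol Section 9.2.2) and has no response threshold, so no formal decision rule is breached. The conclusion rests on the printed definitions, not on the external criteria that the protocol cites.

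**What to change.** 1. In protocol Appendix 11, add to MLFS the condition that no blasts circulate.
2. In Appendix 11, change the marrow limit for CR, CRi, CRp and MLFS from ≤5% to <5%. It then no longer overlaps the ≥5% relapse limit or the lower end of the PR range.
3. Reconcile SAP Section 5.3.1 and the SAP response list with the protocol: primary AML ORR = CR+CRi+CRp+PR, with MLFS reported on a separate line. If the sponsor prefers to keep MLFS, declare the change in SAP Section 6.1 and present ORR with and without it. In that case, also state whether MLFS subjects enter DOR and what ends their response.

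The cost is wording. Blood counts, blast counts and marrow results are already collected. The reported AML ORR may be lower. Once MLFS requires clear blood, it holds only the recently transfused subjects with recovered counts, and they would still be shown on the MLFS line.
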